7.3 Discontinuation of Therapy and Withdrawal of the Patients from the Study

Study therapy should be discontinued and the patient should be withdrawn from the study due to any of the following reasons:

- Informed consent withdrawal (the patient has made the decision to stop the participation in study for any reason)
- The patients require other antibiotic treatment
- Development of any adverse event, including serious adverse event, clinical significant deviation in the laboratory results, or concomitant disease, which at the investigator's opinion indicates, that continuation of the study medication administration is not at the patient's best interest
- Pregnancy
- Termination of the study by the Sponsor (e.g. in case of poor safety results)
- Termination of the study by the Regulatory Authority (e.g. in case of poor safety results).

CONFIDENTIAL Page 36 of 88

In all cases the reason of termination of participation in study must be recorded in eCRF. When the patient is withdrawn from the study, all efforts should be made to perform all procedures scheduled for the "early termination visit":

- if the "early termination visit" coincides in time with scheduled visit the procedures of that visit should be done (Section 9.2);
- if the "early termination visit" coincides in time with unscheduled visit the minimum number of procedures should comply with the "End of treatment visit" (Section 9.2.3).

All the patients withdrawn from the study will receive treatment in accordance with the standards adopted in the hospital.

Withdrawn patients will not be replaced.

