The unblinded person will peel off the outer aluminum band from the top of the glass bottle with Tavanic Placebo (100 ml) solution. The bottle will be packed in a carton with a hole on the bottom for the administration port of the bottle. The carton will be sealed by a sticker to avoid breaking the code. Then, the carton with glass bottle inside will be put into the special designed empty packing box with number "2" on the label. The label with randomization number will be stuck to the box. After that the unblinded person will insert a spike of infusion set into the administration port of the bottle with Tavanic Placebo (100 ml) solution and will prime the infusion set.

Then, a person from blinded staff will take the supply, dose the patient, and return the supply after the dosing to the unblinded staff.

Oral drug dispensing procedure

Neither the patients nor any of the principal investigators (PI)/ co-investigators/ other clinical staff (blinded staff), involved in the treatment of the patients, Sponsor and CRO will be aware of the oral treatment received by the patient.

Since Day 4(8) of the study (switch from i.v. to oral therapy) the patients will receive the blinded capsules of oral drugs according to the medication identification number. Each patient will receive daily treatment with 2 capsules containing either Nemonoxacin (Nemonoxacin 250 mg capsules) or Levofloxacin (Tavanic[®] 250 mg, film coated tablets).

The randomization number will only be broken for an individual patient in an emergency such as an SAE that requires knowledge of which IMP was taken so that the SAE can be treated appropriately. In the event of SAE, if possible, the investigator should contact the medical adviser before the investigational drug blind will be broken to discuss the need for unblinding. If the randomization number for a patient is broken, the investigator must withdraw the patient from the study.

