10.2.2 Clinical response assessment

The investigator will evaluate clinical response to treatment on Day 4(8) of the study (at Visit 2, switch from intravenous to oral therapy), within 1-2 days (Visit 3, end of treatment) and within 7-9 days (Visit 4, test of cure) after the last dose. Criteria for evaluation of clinical response to the therapy are presented in Table 10-1.

Table 10-1 Criteria for evaluation of clinical response

Category	Criteria
Clinical success	 All signs and symptoms of pneumonia presented at Visit 1 (Day 1) are resolved (i.g., resolution of fever, absence of intoxication, purulent sputum, and respiratory insufficiency) or improved with no worsening or appearance of new signs and symptoms of pneumonia. There is no requirement for additional antibiotic therapy. Chest roentgenograms (CT scans) are cured or improved (only for TOC visit).
Clinical failure	 Persistence or worsening in signs and symptoms of the acute process with either failure to show improvement in the clinical findings, initial improvement in signs and symptoms followed by clinically significant worsening before the assessment. Additional antimicrobial therapy required.

CONFIDENTIAL Page 53 of 88

	 Progression (worsening) of chest roentgenogram (CT scans) abnormalities or unchanged chest roentgenogram features (only for TOC visit).
	 Death because of pneumonia.
Indeterminate	• No evaluation possible: the patient was lost to follow-up, or died
	because of noninfectious-related reasons or infection other than
	pneumonia (as judged by the investigator).

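### Sections 7.3 and 8.6 turn listed drug stops and code breaks into study withdrawal, so Visits 4 and 5 are not sought even when no other antibiotic was needed

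*Combined protocol and SAP*

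**What the plan says.** Section 7.3 gives one list of reasons and attaches two consequences to it: "Study therapy should be discontinued and the patient should be withdrawn from the study due to any of the following reasons". Besides consent withdrawal and termination of the study, the list contains "The patients require other antibiotic treatment", pregnancy, and any adverse event, laboratory deviation or concomitant disease for which, in the investigator's opinion, "continuation of the study medication administration is not at the patient's best interest". There is no status for a patient who is off drug but still on study.

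Section 8.6 adds a further route: "If the randomization number for a patient is broken, the investigator must withdraw the patient from the study".

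At withdrawal, section 7.3 asks for an early termination visit. If it falls on a scheduled visit, that visit's procedures apply. If it is unscheduled, "the minimum number of procedures should comply with the" end of treatment visit (Visit 3). Section 7.3 also states: "Withdrawn patients will not be replaced".

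The primary endpoint (5.1.1) is investigator-judged clinical success at Visit 4. In Table 10-1 (10.2.2), success at that visit also requires chest imaging to be cured or improved, and a requirement for additional antimicrobial therapy is clinical failure. Indeterminate is described as "No evaluation possible: the patient was lost to follow-up", or death from a cause other than the pneumonia. Section 12.5 leaves missing data to a statistical analysis plan whose text is not in the file.

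**The concern.** Stopping a drug and leaving a trial are different events. When a protocol merges them, outcome data are missing by rule, in patients selected by tolerability or by an event serious enough to break the code.

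The withdrawn patient's one visit records a clinical response but need not include the imaging that the Visit 4 definition uses. The patient can still belong to mITT, because section 12.1 asks for only one efficacy evaluation. The analyst then has a patient in the primary population without the primary outcome, and Table 10-1 does not clearly say where that patient belongs. A later analysis rule can choose a label for the patient but cannot recover an observation that sites were never asked to make.

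At stake are the direction and size of bias in a non-inferiority comparison. Also at stake is late safety and relapse information, in some of the patients for whom it matters most.

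**Working it through.** **1. Which patients lose what**

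| Reason for leaving | Visit 4 outcome under the current text | After the early termination visit |
|---|---|---|
| Needs another antibiotic | Classifiable as clinical failure (Table 10-1), though no rule carries it to Visit 4 | New AEs/SAEs not sought |
| AE, laboratory deviation, pregnancy or unblinding, with no other antibiotic | Normally not obtained; not clearly classified | New AEs/SAEs and relapse not sought |
| Consent withdrawn or study terminated | Cannot be obtained under any rule | Same |
| Poor compliance | Not a 7.3 reason; a protocol violation (12.2), so Visits 4 and 5 remain due | Unaffected |

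Chest imaging is scheduled only at Visits 1 and 4 (Table 9-1, 10.2.1). The instruction in 9.3 to hold the next visit as scheduled concerns patients who remain in the study. AEs already reported are followed to resolution (11.2), and pregnancies to outcome (11.5).

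**2. Inputs for size**

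From 12.10: success 82% in both arms, margin 15 points, one-sided 5%, 171 randomized per arm and 80% eligible for mITT. 171 × 0.80 = 136.8, which matches the stated 137 per arm. (The printed 5% and 80% power by themselves need about 82 per arm in mITT, so 137 does not follow from them. That is a separate matter, and 137 is used here as the planned size.)

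Half-width of the one-sided 95% interval: 1.645 × √(2 × 0.82 × 0.18 / 137) = 7.6 points.

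**3. Shift if the stopped patients count as non-successes**

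The documents give no withdrawal rate, so the excess of stops in one arm is an assumption. Shift = excess × proportion who would have been successes. That proportion is at most 0.82. If half receive another antibiotic, and so are failures anyway, it is 0.41.

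Power when the excess is on nemonoxacin and the true difference is 0 is Φ((0.15 − shift)/SE − 1.645), with SE = √[((0.82 − shift)(0.18 + shift) + 0.82 × 0.18)/137]. With no shift it is 94%.

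| Excess stops | Patients of 137 | Shift at 0.82 | Power | Shift at 0.41 | Power |
|---|---|---|---|---|---|
| 3 points | 4 | 2.5 | 84% | 1.2 | 90% |
| 5 points | 7 | 4.1 | 73% | 2.1 | 86% |
| 8 points | 11 | 6.6 | 53% | 3.3 | 79% |

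At 8 points and 0.82, SE = 0.0493, and the expected lower bound is −6.6 − 1.645 × 4.93 = −14.7 points against −15.

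**4. Direction**

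- *Counted as non-successes, excess on the comparator.* Take true rates of 67% against 82%, exactly on the margin. A 5-point excess at 0.82 lowers the comparator to 77.9%. The chance of wrongly declaring non-inferiority is then Φ((0.15 − 0.109)/√[(0.67 × 0.33 + 0.779 × 0.221)/137] − 1.645) = 19%, against a nominal 5%.
- *Excluded instead, excess on nemonoxacin.* Take the same true rates, with 10% against 5% withdrawn and all of them true failures (an extreme assumption). Completers show 0.67/0.90 = 74.4% against 0.82/0.95 = 86.3%, and the error is 15.6%. With equal withdrawal of 5% or 10% it is 3.6% or 2.3%, so the inflation comes from imbalance.

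Loss of precision is minor. Excluding 5% to 20% of both arms equally lowers power only from 94.4% to 93.4% to 89.4%.

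**The case against.** A reader might infer that any stop of study drug costs the primary outcome and all later safety data. The documents do not support that. The 7.3 list is closed, and poor compliance is not on it. Patients who need another antibiotic are Table 10-1 failures. Known AEs are still followed. These limits stand, and they confine the point to the second row of the table in step 1.

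The size can also be challenged. The 82% is the planning rate for all of mITT. An inpatient stopped for an adverse event may well be given a replacement antibiotic and then be a failure, unless *additional* therapy is read to exclude a replacement. That is why the upper shifts are maxima and the halved column is shown. Nothing in the documents supports an 8-point excess. Sections 3.3.2.2 and 3.3.2.3 describe adverse events as mostly mild, although the main drug-related findings with intravenous nemonoxacin were infusion-site reactions and raised transaminases, so some imbalance is plausible. Even the largest assumed shift leaves the expected bound just inside the margin.

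Two further inferences go too far. That these patients count as non-successes in mITT is nowhere stated; it is one possible handling. And the clinically evaluable analysis is little affected by 7.3, since 12.2 already removes patients with fewer than 7 days or under 80% of drug. Finally, Visit 3 procedures are a minimum, so a site could image at early termination, but nothing asks it to.

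None of this supplies the missing instruction to follow these patients to Visits 4 and 5.

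**Conclusion.** The point holds in a limited form. By rule, patients withdrawn for an adverse event, laboratory deviation, pregnancy or unblinding, without another antibiotic, normally have no Visit 4 outcome, no clear Table 10-1 category, and no search for new AEs/SAEs or relapse up to Visit 5. The reasons can depend on treatment, so the mITT comparison can be biased. The direction depends on which arm has more stops and on a handling rule that is not in the file.

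The size is not known from the documents. Under the assumed excesses it runs from about 1 to 6.6 points. The upper end needs both an 8-point imbalance and no use of replacement antibiotics. This is a weakness that is cheap to remove, not evidence that the trial would reach a wrong conclusion.

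**What to change.** - **Section 7.3:** separate discontinuing study drug from withdrawing from the study, and leave the reasons for stopping drug unchanged. Only withdrawal of consent or termination of the study ends follow-up. All other patients keep Visit 4, with imaging where clinically permissible (in pregnancy, as the investigator judges), and Visit 5. The existing windows run from the last dose and apply directly.
- **Section 8.6:** replace compulsory study withdrawal after a code break with continued follow-up to Visits 4 and 5. Flag these patients for a sensitivity analysis, because the investigator-judged response is then unblinded. Whether study drug continues after unblinding is for the sponsor to state and reconcile with 7.3; this point takes no position on it.
- **Analysis:** in mITT use the observed Visit 4 response, and carry a Table 10-1 failure, such as need for another antibiotic, forward to Visit 4. State in the SAP how an mITT patient who still lacks Visit 4 is counted, with a sensitivity analysis.

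The cost is protocol wording plus one already-scheduled visit and one telephone call for the few patients affected. The sample size does not change.

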9.2 Description of visits

9.2.1 Visit 1 (screening /randomization and intravenous therapy, Days 1-3(7) of the study)

The Visit 1 is scheduled on Days 1-3(7) of the study and will be performed at hospital. On Day 1 (no more than 24 hours) all screening procedures should be performed and eligible patients should be randomized and after randomization will receive the first intravenous dose of IMP. On Days 2-3(7) patients will receive intravenous therapy.

Therefore during the Visit 1 the following procedures will be performed:

Screening procedures (Day 1)

To evaluate the selection criteria of the study, the Investigator may use laboratory test results obtained at the laboratory of the investigational site within 24 hours of study enrollment (Signing of the Informed Consent Form) if he / she considers that available data are sufficient to permit a decision on whether the subject meets the selection criteria. In this case, another blood sampling procedure has to be conducted in the period from the signing of the Informed Consent Form to the start of treatment in order to evaluate all other laboratory parameters that have to be determined on Day 1 in accordance with the study protocol

- Obtainment of written informed consent (before all other procedures)
- Demographic and other baseline characteristic data collection
- Medical history taking
- Pregnancy test (for women of childbearing potential only)
- Physical examination
- Assessment of vital signs
- ECG (before or 30 minutes after blood samples collection)
- Haematology test
- Biochemical assay
- Urinalysis
- Documentation of SAEs occurred after the obtainment of the informed consent (after the signing of ICF)
- Chest x-ray (two-dimensional roentgenogram) or computed tomography. The results of chest x-ray (computed tomography) performed within 72 hours before enrollment are acceptable
- Pulse oximetry
- Collection of sputum sample for culture (if the patient has sputum)
- Collection of blood sample for culture
- Assessment of prior medication taken within 30 days before the Visit and therapies (beginning from the onset of community-acquired pneumonia)
- Check of inclusion/exclusion criteria

CONFIDENTIAL Page 48 of 88

Randomization and initiation of therapy (Day 1)

- Before starting the therapy patients eligible for inclusion will be randomized
- Start of intravenous therapy with IMP
- Assessment of vital signs 2 hours ± 30 minutes after the second infusion (Tavanic®/Placebo) is finished

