- Documentation of AEs/SAEs occurred after the first IMP administration
- Compliance check
- Assessment of concomitant medication and therapies
- Blood sample collection for PK (via venous catheter): pre-dose, 0 h, 0.5 h (±3min), 2.5h (±5min), 4h (±5min), 6h (±10min), 12h (±15min), 16h (±15min) and 22.5h (±15min) after the end of first infusion (**only for investigational sites defined by the Sponsor**). The last blood sampling for PK (22.5h after the end of the first infusion) should be conducted prior to the IMP infusion on Day 2.

Continuation of intravenous therapy (Days 2-3(7))

All of the following procedures should be performed on each day of Days 2-3(7) of the study:

- Physical examination before dosing
- Assessment of vital signs before dosing
- Intravenous therapy with IMP
- Assessment of vital signs 2 hours ± 30 minutes after the second infusion is finished
- Documentation of AEs/SAEs
- Compliance check
- Assessment of concomitant medication and therapies

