12 STATISTICAL METHODS

12.1 Analysis populations

The following populations will be identified for the statistical analyses:

- Randomized Population (RP): All subjects who were screened and randomized
- Intent-to-Treat Population (ITT): All subjects in the RT population who received at least one complete dose of the drug (Nemonoxacin or Tavanic[®])
- Modified Intent-to-Treat (mITT): Subjects in the ITT population who met the minimal disease criteria (inclusion criteria 3 and 4), and was evaluated for clinical efficacy at least once
- Clinically Evaluable (CE): Per-Protocol subjects in the mITT population (i.e. patients without protocol violations and without a clinical response of "Indeterminate" in the mITT population)
- Bacteriological mITT (b-mITT): Subjects in the mITT population whose bacterial culture yielded at least one baseline bacterial isolate
- Bacteriologically Evaluable (BE): patients in the CE population who had at least one baseline bacterial isolate
- Safety Population (SP): All subjects who received at least one complete dose of the study drug (Nemonoxacin or Tavanic®) and underwent at least one safety evaluation would be included in this data population for safety analysis
- Pharmacokinetic population (PK-C): All subjects who were included in PK study and who had at least 1 measured concentration value.

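### A patient who fails during the i.v. phase can go without any clinical response assessment and so be left out of the mITT primary analysis

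*Combined protocol and SAP*

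**What the plan says.** Section 7.3 lists reasons for stopping study therapy and leaving the study. One is "The patients require other antibiotic treatment". It then gives two rules for the early termination visit. If that visit "coincides in time with scheduled visit the procedures of that visit should be done". If it "coincides in time with unscheduled visit the minimum number of procedures should comply with" the End of treatment visit, the larger set in 9.2.3 applies, and that set includes clinical response.

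Section 9.2.1 states: "The Visit 1 is scheduled on Days 1-3(7) of the study and will be performed at hospital". For the days after Day 1 it says "All of the following procedures should be performed on each day of Days 2-3(7) of the study" and lists physical examination, vital signs, infusion, adverse events, compliance and concomitant medication.

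Section 10.2.2 places the first response assessment later: "The investigator will evaluate clinical response to treatment on Day 4(8) of the study (at Visit 2, switch from intravenous to oral therapy"), followed by Visits 3 and 4. Table 9-1 agrees. Table 10-1 counts both a need for additional antimicrobial therapy and death from pneumonia as clinical failure.

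Section 12.1 limits mITT to ITT patients who met the minimal disease criteria "and was evaluated for clinical efficacy at least once". Section 12.6.2 makes mITT the primary analysis population.

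**The concern.** Read in sequence, these rules let an outcome that arises after randomisation decide who is in the primary denominator. A patient taken off study drug on Day 2 or 3 because it is not working leaves the study on a day whose procedure list contains no response assessment. Nothing requires this patient to attend Visit 3 or 4.

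No other specified efficacy analysis recovers the patient. CE is nested in mITT, and 12.2 makes under 7 days of drug a violation that excludes from CE. Sections 12.6.2 and 12.6.3 specify no efficacy analysis in the ITT population. The patients affected also bear directly on the secondary objective about i.v. efficacy.

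In a non-inferiority trial, losing failures from the arm that has more of them can pull the observed difference towards zero. Section 12.10 expects only 80% of randomised patients in mITT, so about 171 − 137 = 34 per arm are expected outside it. A handful of lost early failures would not stand out.

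**Working it through.** **Which days are affected**

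- Days 1-3 lie inside Visit 1, so the first rule of 7.3 applies. The first response assessment comes later, at Visit 2.
- Days 4-7 of prolonged i.v. therapy depend on what Day 4(8) means. If it is the day of the switch, as the Visit 1 span of Days 1-3(7) suggests, these days still belong to Visit 1 and have no response assessment. If the Visit 2 assessment starts on Day 4 for everyone, they are covered.

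**Inputs from 12.10.** Success rate 82%, margin 15 points, one-sided alpha 5%, 171 randomised per arm, 80% in mITT. The planned mITT size follows: 0.80 × 171 = 136.8, about 137 per arm. Below, 137 serves as the size before the loss in question. That is an assumption, since the plan gives 137 as the size after all exclusions.

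**Same share of failures lost in both arms, Nemonoxacin at the margin**

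True rates are 82% (Tavanic) and 67% (Nemonoxacin). A fraction f of failures in each arm is unscored (assumed). For true rate p:

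- observed rate = p / [1 − f(1 − p)]
- remaining n = 137 × [1 − f(1 − p)]
- P(non-inferiority declared) = Φ[(observed difference + 0.15 − 1.645 × s0) / s1], where s0 is the Farrington-Manning restricted standard error at −15 points and s1 the unrestricted one.

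| f | Nemonoxacin | Tavanic | Difference | False non-inferiority |
|---|---|---|---|---|
| 0 | 67.0% | 82.0% | −15.0 | 5.0% |
| 0.1 | 0.67/0.967 = 69.3% | 0.82/0.982 = 83.5% | −14.2 | 6.8% |
| 0.2 | 0.67/0.934 = 71.7% | 0.82/0.964 = 85.1% | −13.3 | 9.4% |
| 0.3 | 0.67/0.901 = 74.4% | 0.82/0.946 = 86.7% | −12.3 | 13.4% |

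For f = 0.2, s0 and s1 are both about 0.0505, so (0.0167 − 1.645 × 0.0505)/0.0505 = −1.314 and Φ = 9.4%. Replacing the two arm sizes by their harmonic mean gives 6.8%, 9.5% and 13.5%.

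**Selected counts.** All are assumed. Differences are Nemonoxacin minus Tavanic in points, and limits are one-sided 95% lower limits from inverting the Farrington-Manning test.

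| Unscored failures, Nemonoxacin v Tavanic | Kept as failures | Limit | Dropped | Limit |
|---|---|---|---|---|
| 9 v 3 | 102/137 v 113/137, −8.0 | −16.2 | 102/128 v 113/134, −4.6 | −12.6 |
| 9 v 3, two more Nemonoxacin successes | 104/137 v 113/137, −6.6 | −14.6 | 104/128 v 113/134, −3.1 | −10.9 |
| 10 v 3 | 108/137 v 114/137, −4.4 | −12.2 | 108/127 v 114/134, 0.0 | −7.4 |
| 6 v 6 | 102/137 v 113/137, −8.0 | −16.2 | 102/131 v 113/131, −8.4 | −16.2 |
| 3 v 9 | 102/137 v 113/137, −8.0 | −16.2 | 102/134 v 113/128, −12.2 | −19.9 |

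Only the first row changes the conclusion. Equal counts leave the limit where it was, and a loss concentrated on Tavanic moves it against Nemonoxacin. If Tavanic is the worse arm and also loses more failures (113/137 v 102/137, dropping 3 v 9), the limit falls from −0.1 to −3.2, again against Nemonoxacin.

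**The case against.** A reader might infer that every i.v.-phase failure is certain to go unscored and drop out. The documents do not support that, for four reasons.

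- The condition in 12.1 is undefined. Both failure criteria named above are events that need no visit procedure. Section 7.3 requires the reason for termination in the eCRF, concomitant therapy is reviewed daily, and 12.6.3 treats need for another antibiotic as treatment failure. A data manager could reasonably count such a patient as evaluated.
- Section 9.3 allows unscheduled visits at any time for adverse events or medical intervention, and withdrawal at such a visit carries the End of treatment minimum. A site could treat an unplanned withdrawal this way, and nothing forbids an extra assessment. The larger set is therefore not confined to the time after treatment.
- Days 4-7 may be covered, depending on how Day 4(8) is read.
- Section 12.5 leaves missing data to a separate statistical analysis plan, which may settle the classification.

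All four stand as limits on the claim. None of them requires a score. If sites read the rules differently, mITT membership will depend on site practice after randomisation.

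A reader might also infer that the loss always helps the non-inferiority claim. It does not: the 6 v 6 and 3 v 9 rows show otherwise.

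**Conclusion.** The gap is real on the text, most clearly for Days 1-3. A patient who already meets a Table 10-1 failure criterion can be left out of the primary analysis, and no other specified efficacy analysis brings the patient back. The documents do not show that this will happen to every such patient, or how many there will be.

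The bias favours non-inferiority in two situations: unscored failures are more frequent on Nemonoxacin, or a similar share of failures is lost in both arms while Nemonoxacin is truly worse. In the second, with true rates of 82% v 67%, 137 per arm before the loss and 10% to 30% of failures lost, false non-inferiority rises from 5% to about 7% to 13%. The share lost is an assumption, as the plan gives no figure. The 9 v 3 case shows that the conclusion can change, not that it is likely to.

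Because the point concerns the primary denominator and is cheap to close, it should be settled before the database is closed.

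**What to change.** 1. In 7.3, require the 9.2.3 End of treatment assessments, including clinical response, at every early termination, including those on Visit 1 days. Align 9.3 with this.
2. In 12.1, remove the condition of at least one efficacy evaluation from mITT. Alternatively, keep it and state that a patient who meets a Table 10-1 failure criterion before the first assessment is in mITT as Clinical failure at Visit 4.
3. Keep other unscored treated patients in the denominator as Indeterminate, counted as non-success, and add a sensitivity analysis that varies how they are counted. Counting them as non-success can itself shrink the difference: with 10% such patients in each arm at 82% v 67%, the rates become 0.9 × 82 = 73.8% and 0.9 × 67 = 60.3%, and the difference moves from −15.0 to −13.5.

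The cost is a few sentences in the protocol, extra assessments on the withdrawal day for a few inpatients, and possibly slightly lower success rates. No patients or visits are added.
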